**Amendment**

Complete this form and with it, submit any affected IRB materials needing revision. Please provide the entire revised documents (not just revised pages). Protocol amendments must receive IRB review and approval before they are implemented, unless an immediate change is necessary to eliminate an apparent hazard to the subjects.

**The proposed changes associated with this Amendment are related to personnel only (members added or removed from the research team). Subjects do not need to be notified.**

You have completed the Amendment form and can now submit the form.

1. Number of accrued subjects
2. Status of Study (check one):  
 Continuing to accrue study subjects.  
Closed to accrual. Date closed:
3. Special populations (mark as applicable):  
Children (<18 years of age)  
Prisoner population targeted or study participant became a prisoner
4. Summarize the proposed changes to the protocol in lay terms, including the type of change AND what the change involves.  
If this is a change in PI a new Department Chair review is required. Please upload the signed document in the Attachments section.  
Updating healthy participant criteria.  
Adding new recruitment strategy.
5. Provide justification/explanation for the proposed changes.  
Expanding definition of no pain to exclude only those with a meaningful amount of pain to increase recruitment feasibility.  
Adding another recruitment strategy because recruitment efforts have slowed down and want the project to be complete in the award period.
6. For sponsor amendments, when did the SLU site receive  N/A

Protocol Title: Effect of knee pain on walking biomechanics

**notification of changes?**7. Will currently accrued subjects need to be notified of changes? **N****If no, please justify why not.**

Both changes only affect recruitment.

**If yes, please explain how AND when notification or re-consenting will occur.**8. Does the SLU IRB Protocol need to be modified? **Y**9. Are consent documents modified? **N**

Proceed to the appropriate section(s) of the protocol and make your changes. Also make necessary changes in the Consent Form(s), Assent Form(s), Recruitment Statement, or other attachments, as applicable. Use track changes or highlight (in yellow) changes to documents being revised. Please upload a tracked/highlighted copy of each revised document to be stamped upon IRB approval.

**NOTE:** Upload a clean copy (changes or highlights removed) of documents in file formats other than Microsoft Word (i.e., the IRB will remove the tracked changes/highlights on uploaded Word documents).

**NOTE:** Protocol amendments must receive IRB review and approval before they are implemented, unless an immediate change is necessary to eliminate an apparent hazard to the subjects.

**Sponsored Studies:** Remember to update the Sponsor's Protocol version number and date in the Funding section of the protocol (this information will appear on the approval letter).

**List of changed sections:**

Personnel Information

Subject Population 8(a-g)

Subject Population 8(h-k)

Attachments (16)

**Subject Population(s) Checklist**

**Select All That Apply :**

Adults  
Cognitively Impaired Subjects  
Employees (specifically targeted)  
Fetuses  
Minors (under 18)  
Neonates  
Non English Speaking Subjects  
Pregnant Women  
Prisoners  
Students (specifically targeted)  
Terminally Ill Subjects  
Wards of the State  
Other (any population that is not specified above)

---

\*\*\* Study Location \*\*\*

**Study Location(s) Checklist**

**Indicate where the study will be conducted. Select all that apply:**

Saint Louis University, Medical Center Campus  
Saint Louis University, Frost Campus  
Saint Louis University, Madrid Campus  
 Saint Louis University, SLUCare Practice Locations  
SSM STL (DePaul Hospital, St. Mary's Health Center, St. Joseph (St. Charles, Wentzville, Lake Saint Louis), St. Clare)  
Cardinal Glennon Children's Medical Center  
Saint Louis University Hospital (SSM Health- SLU Hospital)  
SLU-SSM Cancer Center Research Alliance Sites  
Other (In the box below, list any off-campus institutions or locations and describe the activities being conducted there. Please provide letters of cooperation and/or IRB approvals from each location to document support/approval of the study. You may provide such documentation as it becomes available, but you may not begin work at those sites until documentation of support is provided to the IRB.) Please refer to the Guidance for involving non-SLU institutions in human subject research.

---

\*\*\* General Checklist \*\*\*

**General Checklist**

Protocol Title: Effect of knee pain on walking biomechanics

**Select All That Apply :**

Collection of Specimens

Data collection via e-mail or the Internet

Deception/Incomplete Disclosure

Dietary Supplements, Vitamins, and Other Food Agents

FDA Approved Device

FDA approved drugs, reagents, other chemicals administered to subjects (even if they are not being studied), or biologic products

Genetic Testing

HIV Testing

Human blood, cells, tissues, or body fluids

International Research or Research on International Populations

Investigational drugs, reagents, chemicals, or biologic products

Investigational Device

Investigator Initiated Study \*?HELP?\*

Medical Records

Photography, Video, or Voice-Recording Subjects

Questionnaires and/or tests

Radioisotopes/radiation-producing machines, even if standard of care

rDNA/Gene Transfer Therapy

Registry(ies)

Specimens to be stored for future research projects (must be in consent form)

Study of existing data or specimens

University Indemnified Study (SLU is responsible for liability coverage) \*?HELP?\*

Other (clarify in text box to the right)

Single Use. Provide a brief summary and justification for the Single Use Therapy. Note: This application will refer to research. For Single Use applications it is understood that 'research' will mean 'therapy'.

**\* \* \* Funding \* \* \*****Funding Checklist****NONE****Funding - Grants/Contracts**

Funding Type	Funded By
Private Agency/Foundation	628
Private Agency/Foundation	628

Protocol Title: Effect of knee pain on walking biomechanics

---

**NOTE:** Applicable grant application, contract or subcontract, investigator's brochure, and sponsor's protocol (for all industry sponsored clinical trials) must be attached. You will be prompted for these in section #16 (Attachments).

---

**\* \* \* Expedited Paragraphs \* \* \***

To request an Expedited Review, check the appropriate category(ies) below. Provide justification for your request for Expedited Review.

To qualify for expedited review, research activities must (1) present no more than minimal risk to human subjects, and (2) involve only procedures listed in one or more of the categories below.

1. Clinical studies of drugs and medical devices only when condition (a) or (b) is met.
  - a) Research on drugs for which an investigational new drug application (21 CFR Part 31, 32) is not required. (Note: Research on marketed drugs that significantly increases the risks or decreases the acceptability of the risks associated with the use of the product is not eligible for expedited review.)
  - b) Research on medical devices for which
    - (i) An investigational device exemption application (21 CFR Part 812) is not required; or
    - (ii) The medical device is cleared/approved for marketing and the medical device is being used in accordance with its cleared/approved labeling.
2. Collection of blood samples by finger stick, heel stick, ear stick, or venipuncture as follows:
  - a) From healthy, nonpregnant adults who weigh at least 110 pounds. For these subjects, the amounts drawn may not exceed 550 ml in an 8-week period and collection may not occur more frequently than 2 times per week; or

From other adults and children, considering the age, weight, and health of the subjects, the collection procedure, the amount of blood to be collected, and the frequency with which it will be collected. For these subjects, the amount drawn may not exceed the lesser of 50 ml or 3 ml per kg in an 8-week period and collection may not occur more frequently than 2 times per week.

Protocol Title: Effect of knee pain on walking biomechanics

---

Children are "persons who have not attained the legal age for consent to treatments or procedures involved in the research, under the applicable law of the jurisdiction in which the research will be conducted."

3. Prospective collection of biological specimens for research purposes by non-invasive means.

**EXAMPLES:** (a) hair and nail clippings in a nondisfiguring manner; (b) deciduous teeth at time of exfoliation or if routine patient care indicates a need for extraction; (c) permanent teeth if routine patient care indicates a need for extraction; (d) excreta and external secretions (including sweat); (e) uncannulated saliva collected either in an unstimulated fashion or stimulated by chewing gumbase or wax or by applying a dilute citric solution to the tongue; (f) placenta removed at delivery; (g) amniotic fluid obtained at the time of rupture of the membrane prior to or during labor; (h) supra-and subgingival dental plaque and calculus, provided the collection procedure is not more invasive than routine prophylactic scaling of the teeth and the process is accomplished in accordance with accepted prophylactic techniques; (i) mucosal and skin cells collected by buccal scraping or swab, skin swab, or mouth washings; (j) sputum collected after saline mist nebulization.

4. Collection of data through non-invasive procedures (not involving general anesthesia or sedation) routinely employed in clinical practice, excluding procedures involving X-rays or microwaves. Where medical devices are employed, they must be cleared/approved for marketing. (Studies intended to evaluate the safety and effectiveness of the medical device are not generally eligible for expedited review, including studies of cleared medical devices for new indications.)

**EXAMPLES:** (a) physical sensors that are applied either to the surface of the body or at a distance and do not involve input of significant amounts of energy into the subject or an invasion of the subjects' privacy; (b) weighing or testing sensory acuity; (c) magnetic resonance imaging; (d) electrocardiography, electroencephalography, thermography, detection of naturally occurring radioactivity, electroretinography, ultrasound, diagnostic infrared imaging, doppler blood flow, and echocardiology; (e) moderate exercise, muscular strength testing, body composition assessment, and flexibility testing where appropriate given the age, weight and health of the individual.

5. Research involving materials (data, documents, records, or specimens) that have been collected, or will be collected solely for nonresearch purposes (such as medical treatment or diagnosis). (NOTE: Some research in this category may be exempt from the HHS regulations for the protection of human subjects. 45CFR 46.101(b)(4). This listing refers only to research that is not exempt.)
6. Collection of data from voice, video, digital, or image recordings made for research purposes.
7. Research on individual or group characteristics or behavior (including, but not limited to, research on perception, cognition, motivation, identity, language, communication, cultural beliefs or practices, and social behavior) or research employing survey, interview, oral history, focus group, program evaluation, human factors evaluation, or quality assurance methodologies. (NOTE: Some research in this category may be exempt from the HHS regulations for the protection of human subjects. 45 CFR 46.101(b)(2) and (b)(3). This listing refers only to research that is not exempt.)
8. [FOR IRB use only]. Continuing review of research previously approved by a convened IRB only when condition (a), (b), or (c) is met.

Protocol Title: Effect of knee pain on walking biomechanics

a) Previously approved research where

- (i) The research is permanently closed to the enrollment of new subjects;
- (ii) All subjects have completed all research-related interventions; and
- (iii) The research remains active only for the long term follow-up of subjects.

b) Previously approved research where no subjects have been enrolled and no additional risks have been identified.

c) Previously approved research where the remaining research activities are limited to data analysis.

9. [FOR IRB use only]. Continuing review or research not conducted under an investigational new drug application or investigational drug exemption where expedited categories two (2) through eight (8) do not apply but the IRB has determined and documented at a convened meeting that the research involves no greater than minimal risk and no additional risks have been identified.

## \* \* \* Background, Purpose, Study Procedures \* \* \*

## Title

Effect of knee pain on walking biomechanics

Complete Sections 1 - 16. In sections that allow reference to sponsor protocol or grant, clearly state section and page numbers. Any information that is different or specific to the local site should be in the SLU application. Specify N/A as appropriate.

## 1. Background

Page numbers from a sponsor's protocol/grant may be referenced in 1a and 1b.

a) Provide an introduction and background information. Describe past experimental and/or clinical findings leading to the formulation of the study, if applicable. Investigator Initiated studies must cite references in the response provided or attach a bibliography. \*?HELP?\*

Osteoarthritis (OA) affects one in eight adults and is a leading cause of disability. Knee OA is particularly prevalent and accounts for an ~83% of the total burden of OA. In many cases, knee OA begins as unilateral disease; yet, up to 90% of those with unilateral knee OA develop bilateral knee OA within 10 years. This is concerning because bilateral KOA is associated with greater functional decline, worse pain, lower quality of life, and higher healthcare costs. To this end, a critical need exists to determine why knee OA commonly progresses from a unilateral to a bilateral disease.

Knee pain may hasten the progression from unilateral to bilateral knee OA if it influences knee joint loads during walking. Those with unilateral knee OA seem to unload their arthritic knee while walking. Although unloading the arthritic knee likely relieves pain, it may shift load to the contralateral knee and increase the risk of bilateral knee OA. However, the speculation that unilateral knee pain influences contralateral knee joint loads while walking remains largely unsubstantiated. Because walking is commonly recommended for managing symptoms of knee OA, it is important to evaluate the effects of unilateral knee pain on contralateral knee loads during walking. Moreover, since walking mechanics are constantly changing with speed, gradient, and fatigue, it is critical to capture the effect of pain on loading during different types of

Protocol Title: Effect of knee pain on walking biomechanics

gradient, and fatigue, it is critical to capture the effect of pain on loading during different types of walking.

Specific Aims as well as Significance Sections for both grants can be reviewed for more information.

References can be found in the attached bibliography or the grant proposals.

**Please save frequently**

b) **Describe any animal experimentation and findings leading to the formulation of the study, if there is no supporting human data.**

N/A

## 2. Purpose of the study

a) **Provide a brief lay summary of the project in <200 words. The lay summary should be readily understandable to the general public.**

Knee osteoarthritis (OA) is a highly prevalent disease that often results in pain and disability. Emerging evidence shows that nearly every person with OA in one knee will develop OA in their other knee within 10 years. This progression is concerning because people with OA in both knees have worse pain, function, and quality of life. The purpose of the current study is to determine if pain in one knee influences loading of the other knee during different types of walking (i.e., varying speeds, gradients, and durations). This project is important because it may lay foundational knowledge that is critical for developing treatments that reduce the likelihood of knee OA progression.

Page numbers from a sponsor's protocol/grant may be referenced in 2b and 2c.

b) **List your research objectives (specific aims & hypotheses of the study).**

Aim 1. Evaluate the effects of unilateral knee pain on contralateral patellofemoral (PF) and tibiofemoral (TF) compartment loads in those with unilateral symptomatic knee OA during level, inclined, and declined walking at comfortable, fast, and slow speeds.

Hypothesis 1.1. Contralateral PF and TF contact forces will be greater during painful walking compared to nonpainful walking.

Hypothesis 1.2. The effect of knee pain on PF and TF contact forces will be greater for inclined and declined walking compared to level walking.

Aim 2. Determine if the presence of unilateral knee pain affects contralateral PF and TF compartment loads during a prolonged walk in those with unilateral symptomatic knee OA.

Hypothesis 2.1. Cumulative loading of the contralateral PF and TF compartments will be greater during a painful 30-minute walk compared to a nonpainful 30-minute walk.

Hypothesis 2.2. Variability of PF and TF contact forces will be greater during a painful 30-minute walk compared to a nonpainful 30-minute walk.

Aim 3. Describe mechanical changes for the hips, knees, and ankles during prolonged walking in those with unilateral symptomatic knee OA.

Hypothesis 3.1. Increased in unilateral knee pain will be associated with decreases in (a) knee work on the painful side, and increases in (b) knee work on the non-painful side, (c) ankle work on both sides, and (d) hip work on both sides.

Protocol Title: Effect of knee pain on walking biomechanics

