**Please save frequently**

c) Describe the study design (e.g., single/double blind, parallel, crossover, control, experimental, observational, etc.). If the study is investigator-initiated, a timeline for individual subject recruitment, follow-up, and analysis for the study is required. Also, indicate if the subjects will be randomized.

This biomechanical study will use a repeated measures design to evaluate the effects of unilateral knee pain on contralateral knee joint loading during different types of walking. Thirty adults with unilateral symptomatic knee osteoarthritis will complete four, 1.5-hour study visits. The first and third visits will include level, inclined, and declined walking at comfortable, fast, and slow speeds. The second and fourth visits will include a 30-minute walk. There will be at least two days between visits. The only difference between each pair of visits is that one visit will involve walking with unilateral knee pain (painful walking) and the other visit will involve walking without unilateral knee pain (nonpainful walking). Individuals will be recruited based on the presence of unilateral knee pain so the painful walking will be representative of their typical walking. For the visits with nonpainful walking, the third and fourth visits, pain will be alleviated by performing an intraarticular injection with a local anesthetic (lidocaine). All walking will be performed in a three-dimensional motion capture environment on a split-belt treadmill that is instrumented with force plates.

A cohort of 30 healthy controls will complete the different walking conditions at two, 1.5-hour study visits. The healthy control group will not receive intraarticular knee injections. The purpose of this cohort is to better understand how walking mechanics in individuals with unilateral knee osteoarthritis compare to similar individuals without knee osteoarthritis.

d) If subjects will be given placebo, please justify placebo use. \*?HELP?\*

N/A

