For the injections, 10 mL of 1% lidocaine hydrochloride will be put into the arthritic knee using a lateral approach. All injections will be sterile and ultrasound-guided to ensure safety and proper placement of drug within the knee joint. Within 5 minutes of the injection, the participant will experience numbness and likely significant decreases in pain. [name] and [name], licensed physicians in the School of Medicine at Saint Louis University, will perform all knee injections and monitor the participant for 15 minutes after the injections.

Walking analysis for those with knee osteoarthritis. At the first and third visits, participants will be asked to complete level, inclined, and declined walking at comfortable, fast, and slow speeds in a randomized order. The only difference between the first and third visits is that an injection of lidocaine hydrochloride will be received during the third visit before walking. Each type of walking will be performed for two minutes then immediately followed by two minutes of rest. For the inclined and declined walking, the treadmill will be set to 8.3% grade (4.8 degrees). This is the maximum gradient for public and business ramps set by the Americans with Disabilities Act, and is therefore representative of gradients that individuals with knee osteoarthritis are exposed to regularly. For the fast and slow walking at each of the gradients, the speed will be increased or decreased 20% of the comfortable walking speed determined during the familiarization walk.

In addition to the first and third visits, which involve nine types of walking, participants will walk for 30-minutes continuously at their second and fourth visits. The only difference between the two 30-minute walks is that an injection of lidocaine hydrochloride will be received during the fourth visit before walking. For these walks, participants will walk at their comfortable speed and 0% grade.

During the 30-minute walks individuals will have a functional near-infrared spectroscopy (fNIRS) cap placed on their head to monitor hemodynamic response in the cortex of the brain. fNIRS utilizes light-emitting diodes and receptors to measure blood oxygenation in the cerebral cortex (the outer portion of the brain). This is similar to how a pulse oximeter measures blood oxygenation in a finger. The overall safety of fNIRS is well established as minimal risk with a similar risk profile to conventional electroencephalography (EEG).

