3. Slipping or falling while walking on the treadmill. Participants will be educated on the use of the treadmill prior to walking. Safety will be ensured by gradually increasing the speed of the treadmill and discussing comfort level. Participants will also wear a fall-safety harness while walking on the treadmill and be instructed to remain within arms-reach of the hand rail. If a participant slips or falls, study staff will stop the treadmill immediately, assess the severity of the slip/fall, and determine if other injuries occurred that require medical attention. First-aid will be provided by study staff as needed. If further immediate attention is needed, an ambulance will be summoned. Regardless of the severity, study staff will follow-up with the participant the following day to ensure appropriate care was received and to determine next steps in study participation.
4. Loss of privacy during data collection. The research lab is accessible to faculty, staff, and students within the Department of Physical Therapy and Athletic Training. It is possible that individuals not directly involved in this study will access the lab during testing. To minimize this risk, signs will be posted outside the lab requesting privacy during testing.
5. Increased knee pain. (Knee OA Cohort only) It is highly likely that participants in the Knee OA Cohort will experience fluctuating pain throughout the study, as this is a typical presentation of knee OA and the protocol is designed to change pain severity. Study staff will closely monitor pain severity throughout the study. If a participant's pain increases to a point where they request to stop walking, testing will be stopped immediately and the participant will not perform any remaining physical tests/procedures. Regardless of pain severity, at the end of each visit, participants will be offered a bag of ice for short-term pain relief.

Protocol Title: Effect of knee pain on walking biomechanics

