6. Skin irritation when removing motion capture markers (i.e., reflective plastic balls). Irritation is generally caused by minor reactions to adhesive or when leg hair is pulled out with the adhesive. This process is comparable to removing a band-aid in a hairy location of the body. In [name] experience, very few people experience irritation that last longer than a few minutes. If a participant experiences lasting irritation, study staff will recommend over-the-counter ointments and determine appropriateness of continued participation.

7. Soreness and/or stiffness in lower body joints and muscles. The study protocol involves walking at different speeds, gradients, and durations. These different types of walking may be unfamiliar to participants and cause soreness and/or stiffness throughout the body, particularly after testing has been completed. This is normal physiologic response to exercise. To reduce the likelihood of excessive soreness or stiffness, participants will be given 2-minute breaks between the different walking conditions. Furthermore, there will be a minimum of 2 days between visits so the likelihood of soreness or stiffness during testing is unlikely. However, if a participant experiences soreness/stiffness that is disabling and either lasts longer or is more severe than expected, study staff will recommend they seek medical attention prior to continuing participation in the study.

8. Loss of confidentiality. In order to protect your information, [name] and the research team will assign you with a subject identifier (unique code), store your personal information (name, date of birth, phone number, email address, and mail address) separate from study data, and only use secure means for collecting, analyzing, and storing your data. Furthermore, after 10 years, your personal information will be destroyed, leaving only de-identified data.

Throughout the study, Research Electronic Data Capture (REDCap) will be used for collecting, managing, and storing your study record. REDCap is a secure web-based tool that is HIPAA compliant and FDA approved. Other than REDCap, raw data files from motion capture and ultrasound imaging will be stored on secure Saint Louis University managed devices with encryption and servers hosted by Saint Louis University's Information Technology Services.

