9. Side effect to lidocaine hydrochloride. Researchers will be using a drug called Lidocaine Hydrochloride to numb the participants knee joint. Although it is unclear how often side effects occur, it is recommended for individuals to seek medical attention if they experience any of the following: Bluish-colored lips, fingernails, or palms blurred or double vision; chest pain or discomfort; cold, clammy, or pale skin; confusion; continuing ringing or buzzing or other unexplained noise in the ears; cough; dark urine; difficulty breathing; difficulty swallowing; dizziness or lightheadedness; dizziness, faintness, or lightheadedness when getting up suddenly from a lying or sitting position; drowsiness; fast heartbeat; fever; headache; hearing loss; hives, itching, skin rash; irregular heartbeat; irregular, fast or slow, or shallow breathing; loss of consciousness; puffiness or swelling of the eyelids or around the eyes, face, lips, or tongue; rapid or slow heart rate; seizures; slow or irregular heartbeat; sore throat; sweating; tightness in the chest; tremor; twitching; unusual bleeding or bruising; unusual tiredness or weakness. There is also the possibility of other side effects. During the study, researchers will monitor the participants closely for any side effects. If any occur, researchers will help them seek immediate medical advice and attention.

10. Discomfort with fNIRS cap. The cap is designed to be snug and the diodes can exert some pressure on the scalp. This improves data quality. The research team will attempt to minimize discomfort by adjusting diode pressures and measuring head size. Although we expect to be able to make adjustments to the cap to minimize discomforts, if a participant reports continued discomfort, fNIRS will not be completed.

Participants may be withdrawn from the research study. Potential reasons for withdrawal include:

- 1) knee pain worsens to a point where alternative treatment is medically indicated
- 2) A side effect or medical condition occurs that may place the participant at risk of further complications
- 3) Inability to participate as instructed
- 4) Inability to keep scheduled appointments
- 5) Cancellation of the research study by sponsor or regulatory agency.

Protocol Title: Effect of knee pain on walking biomechanics

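### Does a 30-minute walk stopped early for pain leave the cumulative-load comparison of Hypothesis 2.1 without a usable rule?

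*Combined protocol and SAP*

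**What the plan says.** Section 2b sets the hypothesis: "Cumulative loading of the contralateral PF and TF compartments will be greater during a painful 30-minute walk compared to a nonpainful 30-minute walk". Section 2c fixes the order: "For the visits with nonpainful walking, the third and fourth visits, pain will be alleviated by performing an intraarticular injection". Visits 1 and 2 are therefore painful, and the pair for Hypothesis 2.1 is visit 2 against visit 4. Section 3b makes both long walks continuous, level and at the participant's comfortable speed. For visits 1 and 3 it says: "Each type of walking will be performed for two minutes then immediately followed by two minutes of rest".

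Section 3d offers descriptive statistics, within- and between-group comparisons, effect sizes and 95% confidence intervals. It does not define cumulative load and does not mention incomplete or missing walks.

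Section 9.9, item 5, says that if pain leads a participant to ask to stop, "testing will be stopped immediately and the participant will not perform any remaining physical tests/procedures". The next sentence of that item offers ice at the end of each visit. Other items in the section speak of what follows: after a fall, staff check the next day "to ensure appropriate care was received and to determine next steps in study participation"; for lasting skin irritation, "study staff will recommend over-the-counter ointments and determine appropriateness of continued participation"; for disabling soreness, "study staff will recommend they seek medical attention prior to continuing participation in the study". The closing list of possible reasons for withdrawal puts first a worsening of knee pain that makes another treatment medically indicated. Its third reason is "Inability to participate as instructed".

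**The concern.** A walk cut short by pain is linked to the exposure under study, so it is not an ordinary missing value. Pain is relieved only at visits 3 and 4, so stops would fall mostly on the painful side of the comparison. If load were summed over whatever minutes were walked, a painful walk stopped early would score low and pull the result against the hypothesis. If such pairs were dropped, the participants least tolerant of pain would leave the analysis.

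The pain-stop sentence also does not say whether it covers that visit or the whole study, although the items on falls, skin irritation and soreness do address continued participation. If it were read as ending participation, a stop at visit 1 or 2 would mean that visit 4 never takes place, and no later analysis can restore that pair.

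**Working it through.** There is no figure in the plan to reproduce: the documents give no power calculation, effect size, SD or stop rate. The check has a reading of the text and an illustration on assumed inputs.

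**Exposure before the first nonpainful walk.** Nine walks of 2 minutes at visit 1 plus 30 minutes at visit 2 give 9 × 2 + 30 = 48 minutes of experimental walking. The familiarization walk at visit 1 adds an unstated amount.

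**Scope of the pain-stop sentence.**
- Item 4 of section 9.9 posts privacy signs during testing, and item 7 speaks of soreness after testing is completed. In both, testing means a session.
- Item 5 itself goes on to speak of the end of each visit.
- The withdrawal list has its own pain criterion, worded differently and discretionary (participants may be withdrawn). A request to stop walking is not on that list.

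Together these favour the reading that the remaining tests are those of that day. The text does not say so outright, and nothing here judges which scope ought to apply.

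**Likely frequency.** Section 8h excludes people who cannot walk 30 minutes without an assistive device, and the walk is level at comfortable speed. Entry pain of at least 3 out of 10 means stops can still happen.

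**Illustration: assumed 30 pairs, 5% effect, SD of the paired difference 9%, two-sided 0.05.**

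*A pair is lost.* If loss falls on those with the most pain, and the load shift has correlation r with pain, the mean moves by −r × SD × (expected sum of the k largest of 30 standard normal values) ÷ (30 − k). That expected sum is 2.04 for k = 1 and 5.02 for k = 3.
- One pair: r = 0 gives 0; r = 0.3 gives −0.3 × 9 × 2.04 ÷ 29 = −0.19 points; r = 0.7 gives −0.44.
- Three pairs: 0, −0.3 × 9 × 5.02 ÷ 27 = −0.50, and −1.17.
- Paired t power from the smaller n alone: 0.837 with 30 pairs, 0.823 with 29, 0.794 with 27. Simulated power when the loss is also informative: one pair, 0.796 (r = 0.3) or 0.768 (r = 0.7); three pairs at r = 0.7, 0.618.

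*A stopped walk is kept as a raw total.* At the same speed and grade, load scales roughly with minutes, so one painful walk stopped at minute T lowers the mean difference by 1.05 × (1 − T/30) ÷ 30.

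| T (minutes) | Drop (points) | Mean difference left |
|---|---|---|
| 10 | 2.33 | 2.67% |
| 15 | 1.75 | 3.25% |
| 20 | 1.17 | 3.83% |
| 25 | 0.58 | 4.42% |

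*Both walks are compared over the same minutes.* With a constant effect the mean stays at 5.0% and power at 0.836 with one to three stops. If the effect grows from 0 to 10% over the walk, the mean is 4.9% with one stop and 4.8% with three.

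So the serious loss comes from one choice, summing over unequal durations. The plan does not make that choice, and the hypothesis, which names two 30-minute walks, gives no support for it.

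**The case for a change.** The strongest case for acting is that the sample is small and the order fixed, so one or two stops could matter. On the assumptions above, one painful walk stopped between minutes 10 and 25 and entered as a raw total cuts power from 84% to 32% by paired t, and from 82% to 65% by Wilcoxon signed-rank. Section 9.9 calls fluctuating pain highly likely. A few sentences would remove the doubt.

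What stands is that the visible text has no load formula, no rule for incomplete walks and no explicit scope for the pain-stop sentence. Stating these would make the write-up clearer.

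The rest is weaker. The 32% needs four things together: a raw-total definition, a stop well before the end, a paired t-test and an effect as small as 5%. A stop at minutes 25 to 30 leaves 78% by paired t, and a 10% effect leaves 97% even with a stop at minutes 10 to 25. The fear that visit 4 is never held depends on the less natural reading of the sentence. The document is an ethics-board application for a funded study. Two grant proposals are attached to it but were not available here; they may define the outcome, though section 3d does not cite them.

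Nor can it be assumed that a rule written now would precede any look at the data. Section 8k plans processing within a week of each collection and analyses from September 2023 to January 2024, and the attachment list runs to March 2024.

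**Conclusion.** No change to the plan follows. This is a gap in detail that analysts fill sensibly: a shortened walk is visible in the data, and comparing its sum with a full 30-minute sum is an error that competent handling avoids. Nothing written in the plan gives a wrong answer. A common-minutes sensitivity analysis and a count of stops would be good reporting, but they would leave the main comparison as it is.

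The size cannot be known from the documents. Under the assumed inputs, one lost pair costs at most about 0.4 points of a 5% effect. Three lost pairs with a strong link between pain and load shift would cost about 1.2 points and bring power to about 62%, but the eligibility criteria make that many stops unlikely. The conclusion rests on stops being few, on the session reading of the pain-stop sentence, and on analysts not comparing totals over unequal minutes. It would need another look if stops proved frequent, or if participants who stopped at visit 1 or 2 were in practice not brought back.
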